TITLE

Occult Paroxysmal Atrial Fibrillation in Non-Cryptogenic Ischemic Stroke

PRINCIPAL INVESTIGATOR:

[name]

CO-INVESTIGATORS:

[name], [name], [name], [name], [name]

CAMPUS:

North Shore University Hospital

INTRODUCTION/BACKGROUND MATERIAL/PRELIMINARY STUDIES AND SIGNIFICANCE

Atrial Fibrillation (AF) is an independent risk factor for stroke.¹ Between 50 and 59 years of age, 1.5% of strokes are attributed to AF, but between 80 and 89 years of age the proportion increases to 23.5%. There are 15 strokes every hour from AF.

Paroxysmal AF (PAF) is sporadic, asymptomatic and has similar risk of stroke when compared to continuous AF.^{2,3} It is not clearly defined in the literature and is more prevalent than persistent AF in patients with ischemic stroke and TIA.⁴ The incidence of paroxysmal AF in cryptogenic stroke is 1 in 6 for age > 55 and 1 in 5 for age > 75.⁵ Most studies based on the prevalence of stroke in the US would suggest that approximately 200,000 individuals may have ischemic stroke associated with PAF. We suspect this number to be higher since long-term monitoring has been restricted only to the cryptogenic stroke population. The risk of stroke recurrence is four times greater among stroke patients with newly detected AF (15.5%) compared to those with either known AF or no AF (3.9%).⁶ Some studies have shown that 5% to 30% of cryptogenic strokes may be due to undetected AF.^{7,8}

The standard Holter monitor has a low sensitivity for detecting paroxysmal AF following an ischemic stroke (approximately 5%). In the recent Crystal AF study, 30% of cryptogenic stroke patients randomized to the Reveal Insertable Cardiac Monitor were found to have PAF compared to 3% of controls over a 3 year monitoring period.^{8,9} There are numerous observational studies that support greater detection of AF with longer monitoring. (Table 1)^{10,11} Median time to AF episode detection was 84 days. Prior studies have shown that long term monitoring for detection of PAF is cost effective.¹² While the relatively high incidence of silent PAF in cryptogenic stroke patients is just now being elucidated, there is no understanding of the frequency of silent PAF in patients with a “known” or presumed etiology for their ischemic stroke other than AF. If this incidence were also found to be significant, a dramatic change in stroke evaluation and management would likely occur.

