- 24-h ECG monitoring for AF detection (eg, Holter monitor or cardiac telemetry)
- TTE and/or TEE
- CTA or MRA of head and neck
- Hypercoagulable blood panel for patients less than 55 years-old
 - Preliminary hypercoagulable work-up within 7 days will include the antiphospholipid antibody syndrome results, which will be needed to determine stroke management. All other results, which could take longer to return, including genetic tests of hypercoagulability, rarely change stroke management.

1. Have virtual CHADS2 score ≥ 3 , or
2. Have 2 or more of the following co-morbidities: obstructive sleep apnea, coronary artery disease, (Chronic Pulmonary Obstructive Disease (COPD), hyperthyroidism, BMI > 30, prior MI, prolonged PR interval (>175 ms) or renal impairment (GFR 30-60).
3. Patient or legally authorized representative who is willing to sign written consent form.
4. Patient is ≥ 40 years old (patients younger than 40 years old have a very low likelihood of having atrial fibrillation and are therefore excluded from the study).
5. Patient can have the device implanted within 10 days of the incident ischemic event

Exclusion Criteria:

1. Documented history of AF or atrial flutter.
2. Evidence of a high-risk cardiac source of embolism (LV or LA thrombus or “smoke,” emboligenic valvular lesion or tumor)
3. Untreated hyperthyroidism.
4. Myocardial infarction or coronary bypass grafting within 1 month prior to the stroke/TIA.
5. Valvular disease requiring immediate surgical intervention.
6. Permanent indication for anticoagulation at enrollment.
7. Permanent oral anticoagulation contraindication.
8. Already included in another clinical trial that will affect the objectives of this study.
9. Life expectancy is less than 1 year.
10. Pregnancy. Urine or serum pregnancy test is required for women of child bearing potential to exclude pregnancy.
11. Patient is indicated for implant with a pacemaker, ICD, CRT device, or an implantable hemodynamic monitoring system
12. Patient is not fit, or is unable or unwilling to follow the required procedures of the Clinical Investigation Plan.
13. Cryptogenic Stroke: A stroke/TIA will be considered cryptogenic if no cause is determined despite extensive inpatient workup (see Inclusion criteria) according to the standard diagnostic protocol at North Shore University Hospital

DESIGN:

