If the patient's decisional capacity is impaired, but the treating Stroke Neurologist deems the patient capable of assenting to study participation, then the patient and their LAR will be included in the informed consent process. In this case, enrollment will proceed only if the patient assents and the LAR gives consent to study enrollment. In the event that the participant is decisionally impaired to the point where both consent and assent cannot be obtained for the study, consent will be obtained from the LAR. In any other situation where the patient is deemed not to have the capacity to consent, the decision will be made not to enroll the patient in the study. All clarifications will be handled directly by the principal investigator.

The use of an LAR will be documented on the data collection form. Enrollment into the study after the informed consent process is completed will be documented in the medical record. In the event that an LAR consents on behalf of a patient lacking capacity, continuing informed consent will be obtained if the treating physician or study physician determines that the patient regains the capacity to consent during the course of the protocol. Assessment for regaining capacity to participate in the informed consent process will be performed at each study visit.

STATISTICAL ANALYSIS

Descriptive statistics (mean \pm standard deviation and median for continuous data such as age; frequencies and percentages for categorical data such as gender, medical history, etc) will be calculated for baseline patient characteristics.

The incidence of AF will be calculated as the total number of patients with AF in 12 months divided by the total number of patients studied, along with the corresponding 95% confidence interval.

The analysis of “time-to-first-documented-AF” will be accomplished by applying standard methods of survival analysis, i.e., computing the Kaplan-Meier¹ product limit curves. In cases where the endpoint event, “AF”, had not yet occurred, 12 months will be used and considered ‘censored’. The median rate will be obtained from the Kaplan-Meier/Product-Limit Estimates and its corresponding 95% confidence interval will be computed, using Greenwood’s formula² to calculate the standard error.

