Univariate analyses will be performed to screen for potential predictors of AF. The chi-square test or Fisher’s exact test, as deemed appropriate, will be used to compare AF patients with non-AF patients for categorical variables and the two-sample t-test or Mann-Whitney test for continuous data.

As a possible secondary analysis, those factors that appear to be associated with AF in the univariate analysis ($p < 0.25$) will be included in a logistic regression model. Backwards selection will be used to remove variables that do not significantly contribute information to the model, given other factors included in the model. A receiver operating characteristic (ROC) curve will be constructed to look at the final model’s ability to predict AF. A numerical measure of the accuracy of the model will be obtained from the area under the curve (AUC), where an area of 1.0 signifies near perfect accuracy, while an area of less than 0.5 indicates that the model is worse than just flipping a coin. The following will be used as a guide for AUC:

0.9-1.0	Excellent
0.8-0.9	Very good
0.7-0.8	Good
0.6-0.7	Average
0.5-0.6	Poor

The Hosmer and Lemeshow Goodness-of-Fit test will also be used to test how well the model fits the data.

Unless otherwise specified, a result will be considered statistically significant at the $p < 0.05$ level of significance. All analyses will be performed using SAS (SAS Institute, Cary, NC).

DISCOMFORTS AND RISKS

The risks to the subjects are low in relation to the anticipated benefits of detecting paroxysmal AF, which will change the strategy of secondary stroke prevention from antiplatelet to anticoagulation

¹ Lee, E. T. (1992), *Statistical Methods for Survival Data Analysis*, Second Edition, New York: John Wiley & Sons.

² Greenwood M. (1926), *The Errors of Sampling of the Survivorship Table*, Vol. 33 of Reports on Public Health and Medical Subjects. London: Her Majesty’s Stationery Office

therapy and reduce the annual risk of recurrent stroke by allowing earlier treatment once AF is detected. The procedural risks have been reviewed under the section (“Design: Reveal LINQ Insertable Cardiac Monitor)

Potential risks and discomforts associated with receiving a Reveal LINQ ICM device include:

- Local site bleeding
- Temporary discomfort at the implant site.
- Rejection of the device by the body, which may have symptoms such as swelling, redness, or other irritation at or near the implant site

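### The optional predictor model's AUC is computed, uncorrected, on the same 75 patients used to select its predictors, so it and its verbal grade are biased upward

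*Combined protocol and SAP*

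**What the plan says.** The relevant text is in the combined protocol and SAP, under Statistical Analysis. AF and non-AF patients are first compared on individual factors. The model is then introduced: "As a possible secondary analysis, those factors that appear to be associated with AF in the univariate analysis" at p<0.25 enter a logistic regression. Next, "Backwards selection will be used to remove variables that do not significantly contribute information to the model". No separate retention level is given, so the general rule, "Unless otherwise specified, a result will be considered statistically significant at the" 0.05 level, appears to govern.

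A ROC curve is drawn for the final model, and "A numerical measure of the accuracy of the model will be obtained from the area under the curve (AUC". A table follows, introduced by "The following will be used as a guide for AUC": 0.5–0.6 Poor, 0.6–0.7 Average, 0.7–0.8 Good, 0.8–0.9 Very good, 0.9–1.0 Excellent. The only other check is the Hosmer–Lemeshow test.

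The design is a single-center cohort of 75. The documents mention no split sample, cross-validation, bootstrap, shrinkage, external data or confidence interval for the AUC. They do not list the candidate predictors.

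**The concern.** An AUC computed on the patients who chose the predictors and fitted the coefficients rewards the model for chance patterns in those patients. The bias is upward on average, although a single realised AUC need not be too high. It grows with fewer events and more candidates. Hosmer–Lemeshow cannot reveal it, because that test looks at fit in the same data.

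The plan treats the AUC as the model's accuracy in predicting AF, and that is a statement about new patients. A model with little or no predictive value could be published as Average or Good, and read as evidence on which patients with non-cryptogenic stroke merit long-term monitoring.

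**Working it through.** The plan states no AUC target, expected AF rate or candidate count, so there is no figure of its own to reproduce. The check simulates the stated procedure.

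**Inputs from the documents.** N = 75; screen at p<0.25; backward logistic selection, retention at p<0.05 by the general rule; AUC on the same 75.

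**Inputs assumed.**
- *AF events:* 8, 15 or 22, i.e. 8/75 = 11%, 15/75 = 20%, 22/75 = 29%. The top end matches the Introduction's figure for a different population over 3 years: "30% of cryptogenic stroke patients randomized to the Reveal Insertable Cardiac Monitor were found to have PAF".
- *Candidates:* 8, 12 or 20, with 5 as a low case. The eligibility criterion beginning "Have 2 or more of the following co-morbidities: obstructive sleep apnea, coronary artery disease" names eight conditions. The virtual CHADS2 score and age are natural additions, as are the baseline variables described as "frequencies and percentages for categorical data such as gender, medical history, etc".
- *Predictors:* independent noise, 70% binary (prevalence 15–50%) and 30% normal. This is a stress test.

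**Rough check.** The chance that at least one of k independent noise candidates reaches p<0.05 is 1 − 0.95^k: 34% for k = 8, 46% for k = 12, 64% for k = 20. The simulated rates of ending with a model (22–30%, 34–43%, 46–61%) lie somewhat below these.

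**Noise-only results.** There were 2,000 studies per cell. The AUC in 2,000 new patients was 0.50 in every cell. The last three columns come from a bootstrap of the whole procedure in 150 surviving noise models per cell, with 100 resamples each:

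corrected AUC = same-data AUC − mean over resamples of (AUC of the resample's model in the resample − its AUC in the original 75).

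A resample with no model counts as zero optimism.

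| Candidates / events | Studies with a model | Mean same-data AUC | All studies with AUC ≥0.70 | Mean corrected AUC | Models with corrected AUC ≥0.70 | All studies, corrected ≥0.70 |
|---|---|---|---|---|---|---|
| 5 / 8 | 12% | 0.73 | 8.7% | – | – | – |
| 5 / 15 | 17% | 0.68 | 3.9% | – | – | – |
| 5 / 22 | 18% | 0.66 | 2.5% | – | – | – |
| 8 / 8 | 22% | 0.73 | 15.5% | 0.67 | 31% | 6.8% |
| 8 / 15 | 26% | 0.69 | 8.4% | 0.61 | 3% | 0.8% |
| 8 / 22 | 30% | 0.67 | 5.9% | 0.59 | 3% | 0.9% |
| 12 / 8 | 34% | 0.75 | 25.8% | 0.65 | 23% | 7.8% |
| 12 / 15 | 38% | 0.70 | 16.8% | 0.59 | 7% | 2.7% |
| 12 / 22 | 43% | 0.68 | 12.2% | 0.58 | 5% | 2.2% |
| 20 / 8 | 46% | 0.77 | 37.0% | 0.65 | 29% | 13.3% |
| 20 / 15 | 57% | 0.72 | 31.6% | 0.59 | 7% | 4.0% |
| 20 / 22 | 61% | 0.70 | 28.0% | 0.57 | 5% | 3.1% |

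The last column is the model rate times the corrected rate, e.g. 0.22 × 0.31 = 6.8%. Monte Carlo error on the bootstrap percentages is up to about 4 points.

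The share of inflation removed is (same-data − corrected)/(same-data − 0.50). It runs from (0.73 − 0.67)/0.23 = 26% (8 candidates, 8 events) to (0.70 − 0.57)/0.20 = 65% (20 candidates, 22 events).

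**With real signal.** A separately coded simulation used AF rates of 10%, 17% and 27%, 10 to 20 candidates and 600 studies per scenario. One third of the candidates were continuous and the rest binary at 30% prevalence.
- *No true predictor:* same-data AUC 0.68–0.78 against 0.50 in new patients.
- *One true predictor (log-odds 0.6 per SD):* 0.72–0.79 against 0.58–0.62, an optimism of 0.10–0.22. Of the fitted models, 58–88% would be graded Good or better, and none reached 0.70 in new patients.

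A further run with one modest true predictor gave 0.72–0.78 against 0.61 in new patients. Bootstrapping the whole procedure brought this to about 0.63 at 15–22 events and 0.71 at 8 events.

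**The case against.** The strongest reply is that little hangs on this. The model is optional. Prediction is neither the primary objective nor one of the four secondary objectives. The incidence and Kaplan–Meier analyses do not use it, no decision rule depends on it, and the grade table is only a guide. All of that stands and limits the consequence. It does not make the AUC right if the model is run, and a guide fed an inflated number gives an inflated grade.

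Second, pure noise is a worst case. The protocol itself links age to the likelihood of AF, and in 39–78% of noise-only studies (8–20 candidates) no variable survives and no AUC is reported. This is fair, and it is why the signal scenarios matter. Optimism is smaller there but still 0.10–0.22, about one grade band or more.

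Third, the inputs are assumed. Real candidates will be correlated, some may be rarer than simulated, and 22 events borrows a 3-year rate in cryptogenic stroke for a 12-month count in another population. With 5 candidates only 2.5–8.7% of noise-only studies reach 0.70. The size is therefore uncertain. The direction was the same in every scenario tested.

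Fourth, the bootstrap correction is only partial, most clearly at about 8 events, where pure noise still averages 0.65–0.67. This also stands. A corrected AUC should not be graded either, and the exploratory label carries much of the protection.

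**Conclusion.** The concern holds. Followed as written, the plan yields an AUC that on average overstates prediction in new patients, and nothing elsewhere in the documents corrects it. Under the assumed 8–22 events and 8–20 candidates, surviving noise models average 0.67–0.77 instead of 0.50, and 6–37% of all noise-only studies would report 0.70 or more. With one modest true predictor (10–20 candidates, AF rates of 10–27%) the excess is 0.10–0.22. These sizes rest on assumed event counts, candidate counts and independent predictors. Fewer than 75 analysed patients would tend to increase the excess.

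This should be corrected if the model is kept. It does not touch the AF incidence estimate or any listed objective.

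**What to change.** If the model is run:

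1. Name the candidate predictors in advance. Without that list the screen cannot be repeated in resamples.
2. Bootstrap the whole procedure, repeating screen, backward selection and fit in each of, say, 500 resamples.
3. Report the optimism-corrected AUC with a 95% confidence interval as the accuracy measure, together with the numbers of AF events and candidates. State that the correction is partial, particularly with about 8 events.
4. Drop the verbal grades, or at the least do not attach them to the uncorrected AUC.
5. Label the model exploratory.

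The cost is modest SAS programming, with no extra patients or data. The sponsor gives up the freedom to choose candidates later and accepts a lower AUC with a visibly wide interval. Items 4 and 5 are wording changes only.

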Device recording of an AF episode of at least 2 minute duration will be required to diagnose a patient with AF. A partial device transmission (summary of potential AF episodes) will be automatically downloaded daily via the Medtronic MyCareLink patient monitor and the study cardiologist will receive an alert within 24-48 hours if the computer monitoring system confirms an episode to be probable AF. Participants may also use the Reveal Patient Assistant to activate recording of cardiac information in the Reveal LINQ ICM while experiencing or immediately after a symptomatic event. Participants will be required to perform a manual device interrogation on a monthly basis. All downloaded rhythms will be manually reviewed every month for each enrolled patient by the study cardiologist. Each AF episode will also be independently adjudicated by a cardiologist blinded to the study protocol.

A total of 75 patients will be enrolled in the study. After enrollment, patients will have study visits at 1, 6, and 12 months. Six and 12 month follow-up visits will be conducted at these time intervals plus or minus 30 days. If the patient cannot come in for a follow-up visit, then the follow-up may be performed as a telephone interview. During the study visits, patients will be assessed for any interval stroke or TIA-like events, intracerebral hemorrhages, interval medical history, device related complications or other adverse events. At the 1-month visit, a NIH stroke scale score will be obtained. At each study visit, a modified Rankin score will be recorded. There will not be any research labs conducted at these study visits and only blood work associated with routine care may be obtained.

Patients will also have one EP cardiology clinical follow-up visit 10 days (plus or minus 4 days) after device implantation to ensure proper healing of the surgical site and functioning of the device.

At the completion of the study, if there is no clinical reason not to remove the device, then the device will be removed at 1 year from implantation. If there is a clinical indication for longer monitoring, then the device will be kept in longer for a maximum of 3 years. However, if clinical monitoring is required beyond the study period, then monitoring will be performed outside of the

study, and the patient or the patient's insurance will be responsible for any clinical fees associated with this post study monitoring.

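### The final model's AUC gets a verbal grade from its point value alone, but for mid-range values at this sample size its 95% CI spans three to five of the 0.1-wide grades

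*Combined protocol and SAP*

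**What the plan says.** All of this is in the Statistical Analysis section of the combined protocol and SAP.

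- **Selection.** For the optional model, "those factors that appear to be associated with AF in the univariate analysis ($p < 0.25$) will be included in a logistic regression model", followed by backward selection.
- **Performance.** A ROC curve is drawn for the final model, and "A numerical measure of the accuracy of the model will be obtained from the area under the curve (AUC").
- **Grading.** "The following will be used as a guide for AUC": 0.5-0.6 Poor, 0.6-0.7 Average, 0.7-0.8 Good, 0.8-0.9 Very good, 0.9-1.0 Excellent. A Hosmer-Lemeshow test is added. No interval is named for the AUC.
- **Contrast.** The same section does plan intervals elsewhere. AF incidence is reported "along with the corresponding 95% confidence interval", and the Kaplan-Meier median also gets one.
- **Size.** "A total of 75 patients will be enrolled in the study" (Design, Follow Up). No expected number of AF cases is given. The Introduction says that the frequency of silent AF in this population is not known.

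**The concern.** The grade table turns one estimate into a word. That is safe only if the sampling error of the AUC is small compared with a band 0.1 wide. Precision here depends mainly on the smaller group, the patients with AF, who may number only one or two dozen. If the 95% CI runs across several bands, a report that follows the plan would call a model Good or Very good when the data are also compatible with lower grades. Readers in a field with no earlier data on this population could then carry the label forward as a finding.

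This does not depend on overfitting. It applies to a score fixed before the study. Screening and backward selection on the same 75 patients add an upward bias on top of it.

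**Working it through.** **Inputs.** From the documents: N = 75, five bands 0.1 wide, selection at p < 0.25 followed by backward elimination. Assumed: m = 8, 15 or 23 AF cases (11%, 20%, 31%), because no AF count is stated. For orientation, the Introduction's cryptogenic-stroke figures of 1 in 6 and 30% (the latter over 3 years) would give about 12 and 22 of 75. The plan has no precision figure to reproduce.

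**Standard error (Hanley-McNeil), with n = 75 − m.**

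SE² = [A(1−A) + (m−1)(a−A²) + (n−1)(b−A²)] / (mn), where a = A/(2−A) and b = 2A²/(1+A).

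At A = 0.75: A² = 0.5625, a = 0.6000, b = 0.6429, so a−A² = 0.0375 and b−A² = 0.0804.

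- 8 vs 67: (0.1875 + 0.2625 + 5.3036)/536 = 0.01073, SE 0.104
- 15 vs 60: (0.1875 + 0.5250 + 4.7411)/900 = 0.00606, SE 0.078
- 23 vs 52: (0.1875 + 0.8250 + 4.0982)/1196 = 0.00427, SE 0.065

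**95% CI = A ± 1.96 SE, cut at 1.0; number of bands overlapped in brackets.**

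| Observed AUC | 8 AF cases | 15 AF cases | 23 AF cases |
|---|---|---|---|
| 0.55 | 0.33-0.77 (3) | 0.38-0.72 (3) | 0.41-0.69 (2) |
| 0.60 | 0.38-0.82 (4) | 0.43-0.77 (3) | 0.46-0.74 (3) |
| 0.65 | 0.43-0.87 (4) | 0.49-0.81 (4) | 0.51-0.79 (3) |
| 0.75 | 0.55-0.95 (5) | 0.60-0.90 (3*) | 0.62-0.88 (3) |
| 0.85 | 0.68-1.00 (4) | 0.72-0.98 (3) | 0.74-0.96 (3) |
| 0.90 | 0.75-1.00 (3) | 0.79-1.00 (3) | 0.81-0.99 (2) |
| 0.95 | 0.84-1.00 (2) | 0.87-1.00 (2) | 0.89-1.00 (2) |

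*Unrounded, 0.597-0.903, which just touches all five.

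On this interval, at least three bands are overlapped in all three scenarios for an AUC between about 0.56 and 0.89. A logit-scale interval with 23 cases moves that range to about 0.57-0.92. With the most favourable split of 75 patients (37 vs 38), an AUC of 0.75 has SE 0.057 and CI 0.64-0.86, still three bands.

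**How often the label is wrong.** Simulation of a fixed binormal score with true AUC 0.75 (correct label Good), 40,000 samples per setting:

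| AF cases | Correct band | Too high | Too low | Within one band |
|---|---|---|---|---|
| 8 | 40% | 31% | 28% | 91% |
| 15 | 52% | 25% | 23% | 97% |
| 23 | 59% | 21% | 20% | 99% |

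The label is therefore wrong in about 60%, 48% and 41% of trials.

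**Why an ordinary interval is not enough.** In a simulation with 12 pure-noise candidate predictors (an assumed number) put through screening and backward selection, the models that kept a factor had a mean apparent AUC of 0.70-0.73. A conventional 95% CI around that value excluded 0.5 in 86-92% of them. The interval has to reflect the selection as well as the sampling error.

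**The case against.** The strongest reply is about weight. The model is only a possible secondary analysis, the bands are offered as a guide, and no objective or decision depends on the grade. The primary result, AF incidence, does have a 95% CI. Nothing forbids adding an interval at reporting. All of that stands and keeps the severity low. It does not remove the point, because the plan states a grading method that uses the point value only.

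Three stronger readings are tempting, and the material does not support them.

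- *The CI always covers at least three grades at 75 patients.* It does not. Near 0.5 and from about 0.9 upward it can cover only two, and the width depends on the AF count, which is not given.
- *The grade is mostly chance, or the data cannot separate Average from Excellent.* With 15 to 23 cases the label is right in just over half of trials and within one band in 97-99%. With 23 cases and an AUC of 0.75 the interval excludes Excellent.
- *The univariate comparisons will mislead because they rest on p-values.* The plan applies a 0.05 level by default, but it screens factors for the model at p < 0.25 and never says that a non-significant factor has no association. Odds-ratio intervals are routine logistic output. Their absence from the text is a matter of reporting detail.

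**Conclusion.** The concern holds in limited form. The plan assigns a verbal grade to the AUC from its point value, and for values of about 0.6 to 0.85 the 95% CI spans three to five of the five grades. A fixed score with true AUC 0.75 is mislabelled in about 40-60% of trials. This rests on an assumed 8 to 23 AF cases among 75, on Hanley-McNeil intervals and on a binormal score. At an AUC of 0.75 the three-band result survives even an equal split. The figures treat the model as fixed, so they leave out the optimism from selecting variables on the same data. Because the analysis is optional and the bands are a guide, the change is desirable but not essential.

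**What to change.** In the Statistical Analysis section, replace the sentence that introduces the AUC guide, and its table, with:

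> The AUC will be reported with a 95% CI from a bootstrap that repeats the p<0.25 screening and backward selection in each resample and corrects for optimism; a verbal grade will be given only if the lower confidence limit reaches that grade.

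The band boundaries would need to be kept in a footnote if grades are still wanted. The program also needs a rule for resamples in which no factor is retained (for example, AUC set to 0.5).

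**Cost.** A little more programming, with the same data and no extra patients or procedures. Model performance will look less definite: by the intervals above, before any optimism correction, an observed 0.75 with 23 AF cases has a lower limit of 0.62 and would be graded Average, not Good.

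As a reporting suggestion only, give odds ratios or differences with 95% CIs beside the univariate p-values.

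### The Hosmer-Lemeshow test, run in the same patients used to build the AF predictor model, cannot detect overfitting, and no other calibration check is planned

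*Combined protocol and SAP*

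**What the plan says.** The Statistical Analysis section introduces the model with the words "As a possible secondary analysis". It is built in two steps. First, "those factors that appear to be associated with AF in the univariate analysis ($p < 0.25$) will be included in a logistic regression model". Then "Backwards selection will be used to remove variables that do not significantly contribute information to the model". No threshold for staying in the model is given, so the general rule presumably applies: "Unless otherwise specified, a result will be considered statistically significant at the $p < 0.05$ level of significance".

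The final model is judged in two ways. One is an ROC curve and its AUC, graded against a verbal scale. The other is this: "The Hosmer and Lemeshow Goodness-of-Fit test will also be used to test how well the model fits the data". The number of risk groups is not stated.

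On sample size, the Follow Up section says: "A total of 75 patients will be enrolled in the study". The document mentions no validation sample, cross-validation, bootstrap, shrinkage or calibration slope.

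**The concern.** The AUC measures discrimination: whether patients with AF are ranked above those without. It does not say whether a predicted risk of 40% means 40%. That leaves Hosmer-Lemeshow as the only planned check on the predicted risks, and it would be made in the data that produced them.

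Screening at p < 0.25 followed by backward selection, with few events, tends to give coefficients that are too large. The model then fits its own patients and predicts risks that are too extreme for anyone else. If a non-significant test is reported as good fit, readers will take it as reassurance on exactly this point, and it gives none.

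**Working it through.** **Inputs.** From the document: n = 75, screening at p < 0.25, backward selection, alpha 0.05, and AF yes or no at 12 months. Not given, and therefore assumed:
- AF rate of 10%, 20% or 30% (the Introduction says the frequency in this population is not known);
- 10, 16 or 20 candidate predictors (the eligibility criteria alone list eight comorbidities, besides the CHADS2 items, age and sex);
- no real predictors, two real predictors (log odds ratio 0.5 each) or four (0.7 each);
- about 10 risk groups, with degrees of freedom equal to groups minus 2.

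The plan states no figure of its own for this test, so there is none to reproduce.

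**Events per candidate.** 75 × 0.10 = 7.5 and 75 × 0.30 = 22.5 events. Per candidate, that is from 7.5/20 ≈ 0.4 to 22.5/10 ≈ 2.3.

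**Why the test is blind.** Maximum likelihood solves Σ(yᵢ − pᵢ) = 0 and Σxᵢ(yᵢ − pᵢ) = 0. Let Lᵢ be the fitted linear predictor. Because L is a linear combination of the x's and the intercept, ΣLᵢ(yᵢ − pᵢ) = 0 as well. These are the score equations for regressing y on L, and they are met at intercept 0 and slope 1. The in-sample calibration slope is therefore exactly 1 whatever n is and however overfitted the model. The Hosmer-Lemeshow statistic, Σ(O − E)²/[E(1 − E/n_g)] over the groups, is referred to a distribution that already allows for fitting in the same data. Redundant predictors do not violate its null hypothesis.

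**Simulation of the planned procedure.** Screen, backward selection at 0.05, test in the same 75 patients, and true slope computed in a large population. There were 27 scenarios of 700 data sets; 18 of them had real predictors. A true slope of 0.25-0.50 means log-odds 1/0.50 = 2 to 1/0.25 = 4 times too spread out.

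| True calibration slope | Passed the test | Rate |
|---|---|---|
| 0.25-0.50 | about 2,487 of 2,637 | 94.3% |
| 0.8 or more | about 510 of 534 | 95.5% |

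The ratio of pass rates is 0.943/0.955 = 0.99, so a pass barely changes the odds that the model is overfitted. By scenario, the pass rate for slopes of 0.25-0.50 was 91-100%. Stay thresholds of 0.10 and 0.25 gave 93-95%. With no real predictors (true slope 0), 90-99% of models still passed.

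**How common such slopes are.** The median true slope was 0.13-0.57 over the 18 scenarios, and 13 of the 18 medians lay in 0.25-0.50.

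**What this means for a risk.** Suppose risks centre on 20% (odds 0.25) and the model predicts 50% (odds 1, four times the centre). At slope 0.50 the true odds are 0.25 × 4^0.50 = 0.50, a risk of 33%. At slope 0.25 they are 0.25 × 4^0.25 = 0.354, a risk of 26%.

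**Is sample size the cause?** With 16 candidates, none real, and 20% AF, the in-sample pass rate was 94.2% at n = 75, 96.6% at n = 300 and 95.7% at n = 1000. By contrast, a fixed model tested in 75 new patients passed 43-81% of the time at twofold spread, 4-49% at threefold and 0.5-27% at fourfold, against 90-96% for correct spread. The blindness comes mainly from testing in the same patients.

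**What the test can see.** In-sample at n = 75, the pass rate was 95-96% for a correct model, 78-79% with moderate omitted curvature, 31-43% with strong omitted curvature and 81-83% with an omitted interaction.

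**Limits.** The test could not be computed for about 3-51% of models by scenario, because the model gave too few distinct risks. At 10% AF, 24-46% of data sets gave no converged model.

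**The case against.** The strongest reply is that the plan asks the test only how well the model fits the data, which is its proper job, and claims nothing about new patients. The model is also optional, no study objective concerns prediction, and nothing says that predicted risks will be reported or used to choose whom to monitor. All of this stands, and it keeps the point minor. It does not remove the gap, because the final model's ability to predict AF is to be graded and this test is the only check beside that grade.

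A reader might infer three stronger claims that are not supported:
- *That a pass carries no information.* It carries some about functional form, as the curvature results show.
- *That 75 patients, or groups of 7 or 8, are the cause.* Pass rates were much the same at n = 300 and 1000, and a correct one-predictor model at n = 75 was rejected 4.0% of the time, so the test's size is acceptable. The small sample makes the overfitting severe; it does not make the test blind to it.
- *That the model will certainly be two to four times too spread out.* That depends on effect sizes the document does not give. In a simpler simulation without selection, at an odds ratio of 2.0 and 20-27% AF, the median slope was 0.72-0.79 with three predictors and 0.58-0.63 with five. The spread is also on the log-odds scale, not in the risks themselves.

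A further objection concerns the remedy: the bootstrap slope under-corrects when predictors are weak. It gave 0.53-0.71 against a true 0.27-0.54 without selection, and about 0.48 against 0.1-0.2 with the planned selection. This stands and limits what the fix may claim.

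**Conclusion.** The point holds in limited form. A non-significant Hosmer-Lemeshow result in these patients says essentially nothing about overfitting. That conclusion follows from the score equations and needs no assumption beyond a maximum-likelihood fit tested in its own data. That the test would use the same patients is inferred from the absence of any other data set in the plan.

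The pass rates and the degree of overfitting do rest on the assumed AF rate, number of candidates and effect sizes. The near-equality of the pass rates was stable over the range tried; the degree of overfitting was not. The 12-month incidence, its confidence interval and the Kaplan-Meier analysis do not depend on the model.

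**What to change.** Replace the Hosmer-Lemeshow sentence with wording such as:

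> The Hosmer-Lemeshow test will be used only as a check of functional form; p > 0.05 will not be taken as evidence of adequate calibration. Calibration slope and AUC will be reported with bootstrap correction for optimism, repeating the p < 0.25 screen and the backward selection in every resample. The corrected slope will be reported as a probably optimistic indicator of overfitting. The model is exploratory.

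Two details belong with it. First, predicted risks should not be presented as corrected merely because they were shrunk by that slope, since it under-corrects here. Second, the plan should say how resamples with no retained variable or with separation are handled. These will be frequent: with 20% AF, 10 candidates and two real predictors, 290 of 700 simulated data sets retained no variable and 38 failed through separation.

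The cost is a few sentences and a short bootstrap program, with no extra patients, visits or data. The downside is a less favourable reported model performance. One paragraph on internal validation can cover both the slope and the AUC.
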